#### 5.1.2 Flow Cytometry Studies for Absolute Numbers and Percentages of Lymphocyte Sets and T-cell Subsets

All FACS samples will be drawn in 10-mL lavender-top tubes and will be performed **during all treatment cycles** as defined in Section 3.8. Labels listing the patient's name, date of birth, date and time of the blood draw will be affixed to all the tubes by the staff person who obtained the samples. The same FACS panels will be performed by the [name] and [name] laboratories for all time points analyzed.

- **Pre-treatment:**

- Two lavender-top tubes drawn for special FACS analysis in the [name] Laboratory (NIAID). Lymphoid Malignancies Branch Clinical Research personnel will arrange for these samples to be sent via courier for cryopreservation to Clinical Support Laboratory [name], [contact] or [contact]).
- One 10 mL lavender top tube Lymphocyte Phenotype IL-15 FACS panel will be drawn and sent via routine collection routing to the Immunology Laboratory of the NIH Clinical Center [name] (to the Attn. of [name] M.D., [contact]) for CD2, CD3, CD4, CD8, CD8 beta, CD11c, CD14, CD16, CD20, CD25, CD27, CD28, CD38, CD45RA, CD45RO, CD56, CD57, CD80, CD86, CD95, IL-2R/IL-15R beta (CD122), CD127 (IL-7R alpha), CD123, CD132, CD62L, CCR5, CCR7, Ki67, IL-15R alpha, and Foxp3.

#### 5.1.3 Inflammatory Markers and Cytokine Analysis

All samples will be drawn in 4 mL SST tubes. Serum samples for these analyses **only during the first treatment cycle** will be obtained from the PK samples (see Section 5.1.1). Labels listing the date and time of the blood draw as well as the patient's name will be affixed to all the tubes by the staff person who obtained the samples. Lymphoid Malignancies Branch Clinical Research personnel will arrange for these samples to be sent via courier to (specified above) the Clinical Support Laboratory, for analysis of IL-2Ra, IL-18, MIP2, MIP1 $\alpha$  and TNF $\alpha$  and to storage for the MesoScale Discovery pro-inflammatory cytokines assay (IL-1 $\beta$ , IL-12p70, interferon  $\gamma$ , IL-6, IL-8 and IL-10).

#### 5.1.4 Anti-IL-15 Antibodies

All samples will be drawn in 4 mL SST tubes; sampling will be performed for the days listed below **during all treatment cycles**. Labels listing the patient's name, date of birth, date and time of the blood draw will be affixed to all the tubes by the staff person who obtained the samples. For questions, please contact [name] Pharmacology Program (CPP) at [contact]; additionally, for pre-notification of planned samples (at least 24 hours in advance, the Friday

before is preferred) email [name] ([[contact]](mailto:[contact])) and [name] ([[contact]](mailto:[contact])). After sample collection, please page [name] for immediate pick-up. For any questions regarding sample processing, you may also contact [name] by e-mail or at [contact].

Samples will be held at room temperature until picked up by the [name] lab (Blood Processing Core) for processing and shipping of the samples to a Contractor for performance of the assays. Lymphoid Malignancies Branch Clinical Research personnel will arrange for these samples to be sent via courier to Clinical Support Laboratory in Frederick (specified above) for assay of the anti-IL-15 antibodies.

Sampling times for the 10-day infusion schedule are as follows:

- **Day 1 pre-treatment, days 12, 28 and off-treatment visit:** One SST tube will be drawn to assess for the formation of anti-IL-15 antibodies.
- Patients will have to demonstrate an absence of anti-IL-15 antibodies in their post-treatment (days 12 and 28) assessments before additional cycles of rhIL-15 can be initiated.

Sampling times for the 5-day infusion schedule are as follows:

- **Day 1 pre-treatment, days 6, 21, day 1 of subsequent cycles and off-treatment visit:** One SST tube will be drawn to assess for the formation of anti-IL-15 antibodies.
- Patients will have to demonstrate an absence of anti-IL-15 antibodies in their post-treatment assessments before additional cycles of rhIL-15 can be initiated.

#### 5.1.5 Optional Tumor Biopsies

Subjects with easily accessible superficial tumor deposits will be asked to sign a separate consent for core biopsies that would be performed by the Department of Radiology and Imaging Sciences' Interventional Radiologists (IR) and evaluated by the NCI Pathology Department at two separate time points [pre-treatment and after treatment has started (anytime from Day 8 to Day 21)] to assess the dynamics of T-cell infiltration and changes in gene expression associated with rhIL-15 treatment. The biopsies should be processed as follows:

- LYMB laboratory staff will provide sample tubes with an adequate amount of RNAlater® for 1 or 2 cores or an excisional biopsy. After the biopsy material is placed in RNAlater®, the specimen will be refrigerated for 12 to 72 hours in [name] prior to being sent via courier to the Clinical Support Laboratory in Frederick for cataloging and long-term storage at -80°C.
- A separate core biopsy (18g) will also be obtained. This sample will be transported to the NCI Pathology Department for confirmation that the specimen contains tumor and for performing routine histologic and immunohistochemical analyses. Alternatively, if fine needle biopsy is performed, the sample will be transported to Cytology.
- If excisional biopsy is performed, [name] will view the size of the specimen to make sure an adequate volume of RNAlater® is used to breakdown tissue/denature proteins and decide if there is an adequate amount of tissue to perform immunohistochemistry.

#### 5.2 SAMPLE STORAGE, TRACKING AND DISPOSITION

Samples will be ordered in CRIS and tracked through a Clinical Trial Data Management system. Should a CRIS screen not be available, the CRIS downtime procedures will be followed. Samples will not be sent outside NIH without IRB notification and an executed MTA.

**5.2.1 Procedures for storage and disposition of serum specimens at the Clinical Support Laboratory, Leidos Biomedical Research, Inc.in Frederick, MD:**

The Clinical Support Laboratory, Leidos Biomedical Research, Inc. processes and cryopreserves samples in support of IRB-approved, NCI clinical trials. All laboratory personnel with access to patient information annually complete the NIH online course in Protection of Human Subjects. The laboratory is CLIA certified for CD4 immunophenotyping and all laboratory areas operate under a Quality Assurance Plan with documented Standard Operating Procedures that are reviewed annually. Laboratory personnel are assessed for competency prior to being permitted to work with patient samples. Efforts to ensure protection of patient information include:

- The laboratory is located in a controlled-access building and laboratory doors are kept locked at all times. Visitors to the laboratory are required to be accompanied by laboratory staff at all times.
- Hard copy records or electronic copies of documents containing patient information are kept in the locked laboratory or other controlled access locations.
- An electronic database is used to store information related to patient samples processed by the laboratory.
- The database resides on a dedicated program server that is kept in a central, locked computer facility.
- The facility is supported by two IT specialists who maintain up to date security features including virus and firewall protection.
- Program access is limited to specified computers as designated by the laboratory director. Each of these computers has a password restricted login screen.
- The database sample entry program itself is accessed through a password protected entry screen.
- The database program has different levels of access approval to limit unauthorized changes to specimen records and the program maintains a sample history.
- Upon specimen receipt, each sample is assigned a unique, sequential laboratory accession ID number. All products generated by the laboratory that will be stored either in the laboratory freezers or at a central repository facility are identified by this accession ID.
- Inventory information will be stored at the vial level and each vial will be labeled with both a sample ID and a vial sequence number.
- Vial labels do not contain any personal identifier information.
- Samples are stored inventoried in locked laboratory freezers and are routinely transferred to the NCI-Frederick repository facilities for long-term storage.
- Access to stored clinical samples is restricted. Investigators establish sample collections under “Source Codes” and the investigator responsible for the collections, typically the protocol Principal Investigator, specifies who has access to the collection.
- Specific permissions will be required to view, input or withdraw samples from a collection. Sample withdrawal requests submitted to approved laboratory staff by anyone other than the repository source code owner are submitted to the source code owner for approval. The repository facility will also notify the Source Code holder of any submitted requests for sample withdrawal.
- It is the responsibility of the Source Code holder (generally the NCI Principal Investigator) to ensure that samples requested and approved for withdrawal are being used in a manner consistent with IRB approval.

- The Clinical Support Laboratory in Frederick does perform testing services that may be requested by clinical investigators including, but not limited to, immunophenotyping by flow cytometry and cytokine testing using ELISA or multiplex platforms.
- When requests are submitted by the NCI investigator for shipment of samples outside of the NIH it is the policy of the laboratory to request documentation that a Material Transfer Agreement is in place that covers the specimen transfer. The laboratory does not provide patient identifier information as part of the transfer process but may, at the discretion of the NCI investigator, group samples from individual patients when that is critical to the testing process.
- The NCI investigator responsible for the sample collection is responsible for ensuring appropriate IRB approvals are in place and that a Material Transfer Agreement has been executed prior to requesting the laboratory to ship samples outside of the NIH.

**5.2.2 Sample Handling, Data Collection and Sample Disposition for the Blood Processing Core ([name] Lab)**

- The samples will be processed, barcoded, and stored in [name] lab until requested by the investigator.
- All samples sent to the Blood Processing Core (BPC) will be barcoded, with data entered and stored in the LABrador (a.k.a. LabSamples) utilized by the BPC. This is a secure program, with access to LABrador limited to defined BPC personnel, who are issued individual user accounts. Installation of LABrador is limited to computers specified by [name]. These computers all have a password restricted login screen. All BPC personnel with access to patient information annually complete the NIH online Protection of Human Subjects course.
- LABrador creates a unique barcode ID for every sample and sample box, which cannot be traced back to patients without LABrador access. The data recorded for each sample includes the patient ID, name, trial name/protocol number, time drawn, cycle time point, dose, material type, as well as box and freezer location. Patient demographics associated with the clinical center patient number are provided in the system. For each sample, there are notes associated with the processing method (delay in sample processing, storage conditions on the ward, etc.).
- Following completion of this study, samples will remain in storage as detailed above. Access to these samples will only be granted following IRB approval of an additional protocol, granting the rights to use the material.
- Sample barcodes are linked to patient demographics and limited clinical information. This information will only be provided to investigators listed on this protocol, via registered use of LABrador. It is critical that the sample remains linked to patient information such as race, age, dates of diagnosis and death, and histological information about the tumor, in order to correlate genotype with these variables.

**5.2.3 Disposition of samples**

- All specimens obtained in the protocol are used as defined in the protocol. Any specimens that are remaining at the completion of the protocol will be stored in the conditions described above. The study will remain open so long as sample or data analysis continues. Samples from consenting subjects will be stored until they are no longer of scientific value or if a subject withdraws consent for their continued use, at which time they will be destroyed. The PI will report any loss or destruction of samples

- to the NCI IRB as soon as he is made aware of such loss
- Blood and tissue specimens collected in the course of this research project may be banked and used in the future to investigate new scientific questions related to this study. However, this research may only be done if the risks of the new questions were covered in the consent document and the proposed research has undergone prospective IRB review and approval. If new risks are associated with the research (e.g., analysis of germline genetic mutations), the Principal Investigator must amend the protocol and obtain informed consent from all research subjects.
- Once primary research objectives for the protocol are achieved, intramural researchers can request access to remaining samples provided they have an IRB-approved protocol and subject consent. Access to these samples will only be granted following IRB approval of an additional protocol, granting the rights to use the material.
- Samples will be stored for future use following completion of the study in only those subjects who have consented to do so in the Optional Studies section of the Consent Document.
- If, at any time, a subject withdraws from the study and does not wish for their existing samples to be utilized, the individual must provide a written request. Following receipt of this request, the samples will be destroyed (or returned to the subject, if so requested), and reported as such to the IRB.
- The PI will report destroyed samples to the IRB if samples become unsalvageable because of environmental factors (ex. broken freezer or lack of dry ice in a shipping container) or if a patient withdraws consent. Samples will also be reported as lost if they are lost in transit between facilities or misplaced by a researcher. Freezer problems, lost samples or other problems associated with samples will also be reported to the IRB, the NCI Clinical Director, and the office of the CCR, NCI.

## **6 DATA COLLECTION AND EVALUATION**

### **6.1 DATA COLLECTION**

The PI will be responsible for overseeing entry of data into an in-house password protected electronic system and ensuring data accuracy, consistency and timeliness. The principal investigator, associate investigators/research nurses and/or a contracted data manager will assist with the data management efforts. All data obtained during the conduct of the protocol will be kept in secure network drives or in approved alternative sites that comply with NIH security standards. Primary and final analyzed data will have identifiers so that research data can be attributed to an individual human subject participant.

All adverse events, including clinically significant abnormal findings on laboratory evaluations, regardless of severity, will be followed until return to baseline or stabilization of event. Patients will be followed for adverse events for at least 30 days after removal from study treatment or until off-study, whichever comes first.

An abnormal laboratory value will be recorded in the database as an **AE only** if the laboratory abnormality is characterized by any of the following:

- Results in discontinuation from the study
- Is associated with clinical signs or symptoms
- Requires treatment or any other therapeutic intervention

- Is associated with death or another serious adverse event, including hospitalization.
- Is judged by the Investigator to be of significant clinical impact
- If any abnormal laboratory result is considered clinically significant, the investigator will provide details about the action taken with respect to the test drug and about the patient's outcome.

**End of study procedures:** Data will be stored according to HHS, FDA regulations and NIH Intramural Records Retention Schedule as applicable.

**Loss or destruction of data:** Should we become aware that a major breach in our plan to protect subject confidentiality and trial data has occurred, the IRB will be notified.

## **6.2 RESPONSE CRITERIA**

### **6.2.1 Radiographic Evaluation and Laboratory Assessments for Clinical Responses**

- All patients will have repeat baseline radiologic studies to assess marker lesions (measurable) and evaluable lesions (non-measurable) performed on day 28 ± 3 days of each treatment cycle for comparison to their pre-treatment studies.
- Patients with evidence of a partial or complete response (RECIST criteria) may undergo a confirmatory scan that will be performed at least 4 weeks after the scan which first met the criteria for a clinical response to rhIL-15 treatment.
- Appropriate patients with tumors known to have tumor markers (PSA, CEA, and CA125) will have the serum level of these markers assessed at the time of their radiographic restaging to gain further insight into the potential efficacy of rhIL-15 treatment.

### **6.2.2 Solid Tumors**

Response and progression for all solid tumors with the exception of non-Hodgkin's lymphomas will be evaluated in this study using the new international criteria proposed by the revised Response Evaluation Criteria in Solid Tumors (RECIST) guideline (version 1.1) ([70](#)). Changes in the largest diameter (unidimensional measurement) of the tumor lesions and the shortest diameter in the case of malignant lymph nodes are used in the RECIST criteria.

#### **6.2.2.1 Definitions**

Evaluable for toxicity: All patients will be evaluable for toxicity from the time of their first treatment with rhIL-15.

Evaluable for objective response: Only those patients who have measurable disease present at baseline, have received at least one cycle of therapy, and have had their disease re-evaluated will be considered evaluable for response. These patients will have their response classified according to the definitions stated below. (Note: Patients who exhibit objective disease progression prior to the end of cycle 1 will also be considered evaluable.)

Evaluable Non-Target Disease Response: Patients who have lesions present at baseline that are evaluable but do not meet the definitions of measurable disease, have received at least one cycle of therapy, and have had their disease re-evaluated will be considered evaluable for non-target disease. The response assessment is based on the presence, absence, or unequivocal progression of the lesions.

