### 3.2.1 DLT will be defined as follows:

Grade 2 diarrhea lasting more than 24 hours or any grade 3 or 4 toxicity, if deemed possibly, probably or definitely related to the study drug by the PI during the first cycle of treatment, **with the following exceptions:**

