3. Denotes testing to be performed at an end of study visit (just prior to the patient being taken off study), if feasible.
4. Because the treatment is CIV for 120 hours, the day 5 treatment concludes on day 6.
5. Interval history during inpatient treatment period.
6. Vital signs, including heart rate, blood pressure, respiration, temperature and arterial oxygen saturation (SO2) by transcutaneous pulse oximeter.
  - a. Every 4 hours  $\pm$  1 hour during treatment days 1 through 6 (SO2 every 8 hours  $\pm$  1 hour)
  - b. Every 8 hours  $\pm$  1 hour on other inpatient days
  - c. Once at outpatient clinic follow-up visits on days 8 and 21.
  - d. Off treatment visit
  - e. End of study visit.
7. Repeat radiologic studies to assess response the last week (day 14 through 21) of even numbered cycles (2, 4, 6 and so on) as long as patients meet criteria to continue treatment. Patients with evidence of a partial or complete response (RECIST criteria) may undergo a confirmatory scan at least 4 weeks after the scan which first met the criteria for a clinical response. Patients with tumors known to have tumor markers (PSA, CEA, and CA125) will have the serum level of these markers assessed at the time of their radiographic restaging.
8. Pretreatment on Day 1 or within 3 days of starting treatment in women of child bearing potential.
9. PKs are collected on Cycle 1 only. Samples are collected in 4 mL SST tubes at the time points. These samples will be held at room temperature until picked up by the [name] laboratory (Blood Processing Core) for processing ([contact] for pickup). See Section [5.1](#) for additional details.
10. One 10 mL lavender-top tube will be drawn for Lymphocyte Phenotype IL-15 FACS analysis. If the Immunology Section Laboratory is unable to perform this analysis on the specified days, this assessment maybe omitted or replaced with standard TBNK panel. See Section [5.1.2](#) for additional details:
  - a. At baseline (need to perform twice before initiating study drug if at all possible.)
  - b. Day 1: prior to the start of the CIV rhIL-15 infusion
  - c. Days 8 and 21 drawn with the routine laboratories
11. Two 10 mL lavender-top tubes will be drawn for the [name] Lab (NIAID) to perform special FACS analysis. See Section [5.1.2](#) for additional details:
  - a. At baseline (need to perform twice before initiating study drug if at all possible.)
  - b. Day 1: prior to the start of the CIV rhIL-15 infusion

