#### **3.10.1 Off-Treatment Criteria**

- DLT as defined in Section [3.2](#).
- Persistent (> 14 days) treatment-related grade 2 (non-DLT) adverse events.
- Completion of protocol therapy
- Patient requests to be withdrawn from active therapy.
- Disease progression.
- No evidence of clinical response (i.e., patient has stable disease) on radiographic restaging after 2 consecutive cycles of treatment.
- The detection of anti-IL-15 neutralizing antibody serum titer  $\geq 500$  ng/mL as described in [APPENDIX C](#) prior to subsequent treatment cycles.
- Evidence the patient has developed auto-immunity that involves a vital organ (heart, kidney, brain, eye, thyroid or adrenal gland, colon, lung). Patients who develop new auto-antibodies without clinical evidence of end organ dysfunction will be seen by the appropriate Internal Medicine subspecialists to assess their risk for developing an autoimmune syndrome.
- Interruption of CIV rhIL-15 treatment for any reason for more than 24 consecutive hours during cycle 1. Stoppage of less than 15 minutes occurring during the daily change of the rhIL-15 infusion device will not be considered an interruption.
- Positive pregnancy test

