## **8 STATISTICAL CONSIDERATIONS**

The primary objective of this trial is to determine the safety, toxicity profile, DLT and MTD of CIV rhIL-15 administered for 10 consecutive days (240 hours) or 5 consecutive days (120 hours) in subjects with metastatic unresectable cancers for which curative or palliative measures either do not exist or are not associated with a survival advantage.

The secondary objectives include determination of rhIL-15 PK, including time to reach serum steady state, decline if any at later time points, changes in serum concentration associated with the expected lymphocytosis and decline following discontinuation of the CIV infusion; characterization of the biological effects of rhIL-15 on the percentages and absolute numbers of circulating lymphocyte sets (NK and T-cells) and T-cell subsets (naïve, central or effector memory subsets based on expression of CD56, CD4, CD8, CD45RO, CD45RA, CD28, CD95, CCR7 and CD62L) by flow cytometry and the plasma levels of pro-inflammatory cytokines. The potential antitumor activity of rhIL-15 will be assessed by the clinical response rate and time to progression in this patient population; and assessment of the nature of T-cell infiltration and cytokine and check-point inhibitor gene expression by analysis of pre- and post-treatment biopsies obtained from selected patients with easily accessible tumor deposits. All evaluations of these secondary endpoints will be considered exploratory.

There are 9 planned dose levels for this trial that will enroll 3 to 6 patients each using a modified Fibonacci design to define the MTD for CIV rhIL-15.

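### The response-evaluable set can drop treated patients who stop in cycle 1 without imaged progression, which biases the exploratory response rate upward

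*Combined protocol and SAP*

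**What the plan says.** Section 6.2.2.1, within the solid-tumour criteria, sets two different populations. For toxicity: "All patients will be evaluable for toxicity from the time of their first treatment with rhIL-15". For objective response: "Only those patients who have measurable disease present at baseline, have received at least one cycle of therapy". The same sentence goes on to require a repeat disease assessment. A note adds one exception: "Patients who exhibit objective disease progression prior to the end of cycle 1 will also be considered evaluable".

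Other sections bear on who meets that rule:

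- Section 3.2.1 counts a listed toxicity as dose-limiting "if deemed possibly, probably or definitely related to the study drug by the PI during the first cycle of treatment". Section 3.10.1 opens its reasons for stopping treatment with "DLT as defined in Section" 3.2.
- For the 5-day schedule, footnote 7 of Section 3.8.2 says: "Repeat radiologic studies to assess response the last week (day 14 through 21) of even numbered cycles", for patients who still qualify to continue. The calendar also appears to mark tumour imaging at the End of Treatment visit, which footnote 16 places about 30 days after the last dose.
- Section 3.1 plans restaging for patients who stop because of toxicity. For the 10-day schedule it plans scans in week 4 of cycles 1 and 2 and at the off-treatment and off-study visits.
- Section 8 says: "The potential antitumor activity of rhIL-15 will be assessed by the clinical response rate and time to progression". It calls the secondary evaluations exploratory. It names no denominator for the rate, no rule for unassessed patients and no confidence interval.

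**The concern.** Membership of the response set depends on what happens after treatment starts, and the rule treats two kinds of early failure differently. A patient whose disease progresses on imaging in cycle 1 stays in the denominator as a non-responder. A patient who stops in cycle 1 for toxicity, withdraws, dies or deteriorates without imaged progression can disappear from it. Such patients have had almost no chance to be recorded as responders, so removing them raises the rate.

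What is at stake is the description of clinical activity. Section 8 gives that as the reason for treating up to nine patients at the MTD or maximum administered dose on each schedule. In a group that small, one or two exclusions visibly change the percentage a reader takes away.

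**Working it through.** **Step 1: apply the rule to each early exit.**

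- Objective progression before the end of cycle 1: counted, by the exception.
- DLT during the infusion, treatment stopped, no progression imaged in cycle 1: not counted unless a partial infusion qualifies as one cycle, which the text does not say. A later scan meets only the re-evaluation condition.
- DLT after the full infusion, then rescanned: can be counted.
- Withdrawal, death or symptomatic deterioration in cycle 1 without imaged progression: not counted if the one-cycle condition fails or no scan is done. The table notes in Section 6.2.2.6 treat symptomatic deterioration as separate from objective progression, so the exception does not cover it.
- 5-day patient who completes cycle 1 but leaves before the first routine scan: counted only if imaged elsewhere, for example at End of Treatment. That routine scan falls on study day 21 + 14 = 35 to 21 + 21 = 42.

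**Step 2: inputs.** The plan states no response rate to reproduce. Its accrual figures do reproduce: 24 + 2 + 6 + 6 + 9 = 47 evaluable, and 47 + 5 = 52 with the allowance for inevaluable patients. N = 9 is the planned total at the MTD or maximum administered dose (Schema, Section 8). The number of responders x and the number dropped d are not in the documents and are assumed here. As a guide to d, 5/52 = 9.6%, and 9 × 5/52 = 0.87, or about one patient in nine.

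**Step 3: formula.** All-treated rate = x/N. Evaluable-set rate = x/(N−d), if all d dropped patients are non-responders. Ratio = N/(N−d).

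**Step 4: N = 9, x = 1, with exact (Clopper-Pearson) 95% intervals.**

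| Dropped d | Rate | 95% CI | Ratio |
|---|---|---|---|
| 0 | 1/9 = 11.1% | 0.3–48.2% | 1.00 |
| 1 | 1/8 = 12.5% | 0.3–52.7% | 1.13 |
| 2 | 1/7 = 14.3% | 0.4–57.9% | 1.29 |
| 3 | 1/6 = 16.7% | 0.4–64.1% | 1.50 |

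With x = 2 the same steps give 22.2%, 25.0%, 28.6% and 33.3%. With x = 0 the rate is 0% under either denominator.

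**Step 5: variants.**

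- Replacement. Sections 3.3 and 8 replace patients without a DLT who do not finish a cycle. With one such patient, ten are treated and nine evaluable: 1/10 = 10.0% against 1/9 = 11.1%. With two, 1/11 = 9.1% against 11.1%. Patients with a DLT are not replaced, so Step 4 applies to them.
- Whole trial, assuming x = 4. Of 47 treated, 4/47 = 8.5% becomes 4/44 = 9.1% with three dropped, 4/42 = 9.5% with five and 4/37 = 10.8% with ten. Of 52 treated with five dropped, 4/52 = 7.7% becomes 4/47 = 8.5%.

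**The case against.** The strongest reply is that the plan does provide imaging after early stops, and that little turns on the rate.

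- **Imaging.** Footnote 7 of Section 3.8.2 might lead a reader to infer that anyone leaving the 5-day schedule before week 5 is never scanned. The documents do not support that: End of Treatment imaging appears in the calendar, Section 3.1 plans restaging after toxicity stops, and Section 3.6.8 allows extra scans when progression is suspected. This weakens the re-evaluation part of the concern. It does not touch the separate one-cycle condition, and footnote 16 allows local laboratory tests or a telephone assessment when a patient cannot return.
- **Toxicity failures.** A reader might infer that all of them are excluded. The text requires one cycle without defining it, and a DLT after a completed infusion need not breach the condition. So exclusion is possible, not certain. The undefined term also leaves the choice open until outcomes are known.
- **Dose.** A reader might infer that the bias is worst in the expansion cohort because it sits at the highest, least tolerated dose. On the 10-day schedule the MTD is 2 mcg/kg/day, below the 4 mcg/kg/day level tested, and an MTD allows at most 1 DLT in 6. The 5-day expansion could be at the top dose only if no MTD is reached.
- **Size.** Two or three losses in nine exceed the plan's own allowance, and the exact interval for 1/9 is far wider than the shift. Both points stand. But a wide interval does not remove a bias of known direction.
- **Consequence.** The endpoint is exploratory, no target rate is set, and the 5-day expansion opens on a count of confirmed responders. This stands and limits the point to reporting.

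**Conclusion.** The point holds as a reporting bias. Followed as written, Section 6.2.2.1 can remove treated non-responders after treatment has begun, and no section supplies an all-treated rate to set beside the result. For one responder among nine treated, the likely effect is 11.1% reported as 12.5%. The figures of 14.3% and 16.7% need two or three exclusions, the last being an upper illustration.

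This rests on assumed counts and on the dropped patients being non-responders. That will nearly always be so, but a patient who stopped mid-infusion and later responded would also be excluded, and that would lower the rate. There is no effect if nobody responds.

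A reader should not infer that dose finding is compromised. MTD decisions use DLT counts, and the 5-day expansion gate uses a responder count with no denominator.

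**What to change.** In Sections 6.2.2.1 and 8:

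1. Make all treated patients with measurable disease at baseline the main denominator for the response rate, and count those without a post-baseline assessment as non-responders. Measurable disease can stay as a condition because it is fixed before treatment.
2. Report this rate by schedule and at the MTD or maximum administered dose, with exact 95% confidence intervals. For three-patient cohorts, give counts only.
3. Keep the evaluable-set rate as supportive. State whether at least one cycle means the full infusion, any part of it or the whole cycle period, and list the reason for each exclusion.
4. State the corresponding set for lymphoma, since the current definition sits in the solid-tumour section.
5. Reconcile the restaging times: Section 6.2.1 asks for scans around day 28 of each cycle, which does not fit a 21-day cycle or the 5-day calendar.

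The cost is a few sentences and an extra table column, with no added patients or procedures. The downside is that the main rate will look slightly lower.
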